10.6.7 Sensitivity analyses

To assess the robustness of our results we will explore the effect of alternative imputations of missing data on the primary analysis. These include:

- 1) Best Case:
All missing 6-month data are coded success (Primary Patency = 1).
- 2) Worst Case:
All missing 6-month data (including those patients for whom there is no post-procedure Primary Patency measurement) are coded failure (Primary Patency = 0).
- 3) Tipping Point:
Worst case imputations will be applied sequentially to missing cases until that point where the result becomes non-significant.

10.6.8 Covariate analyses

Covariate analyses for the dichotomous primary endpoint will be done using logistic regression, where the dependent variable is subject's score on the endpoint and independent variable is the covariate.

For the above we will be comparing device performance between levels defined on the covariate (e.g. male vs. female for the Gender covariate). It should be noted that much of the pertinent information will likely be obtained from descriptive statistics since this trial is not powered to demonstrate subgroup differences.

The following covariates will be tested:

Document title:
VasQ FDA pivotal Protocol

Document No.
CD0121

Revision
12.0
14 March 2021

Page
40 of 42

- Gender
- Age
- Ethnicity
- Whether or not had previous fistula failure
- Dialysis status
- Diabetes
- Hypertension
- BMI
- Baseline artery/vein diameter

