6 ENDPOINTS

6.1 Primary effectiveness endpoint

The primary effectiveness endpoint is primary patency at 6 months post AVF creation. Fistulas are defined as primarily patent¹ if they are free from any intervention up to 180 days (endovascular or surgical) to maintain or restore blood flow and demonstrate minimum flow on Doppler or palpable thrill and audible bruit or are receiving dialysis through the fistula.

- The flow criterion is adapted to a range consistent with a documented² interobserver and intraobserver variability, with various ultrasound systems.
- Due to the COVID-19 pandemic, patients are more prone to miss their on-site doppler examination at 6 months, but still undergo access site assessment (i.e. thrill palpation and bruit evaluations) which is a valid assessment for confirmation of patency (Shenoy et al.). Thus, patients that have bruit and thrill data indicating patency or actively receiving dialysis through the fistula at 6 months without interventions, will be considered as success.

1 = Success = Intervention free access patency at 180 days. Confirmation of fistula patency is established by meeting one of the following three conditions:

1. Artery or vein flow ≥ 500 (-50) ml/min determined by Doppler ultrasound.
or
2. Clinical assessment of palpable Thrill and audible bruit at 6 months
or
3. Patient is receiving dialysis through the fistula at 6 months

Note: if patient is not receiving dialysis through the fistula at 6 months, this will not indicate failure.

0 = Failure = Access underwent intervention before 180 days
or

¹ Shenoy, Surendra, et al. "Clinical trial end points for hemodialysis vascular access: background, rationale, and definitions." Clinical Journal of the American Society of Nephrology 13.3 (2018): 490-494.

² Hoyt Kenneth et al. Accuracy of Volumetric Flow Rate Measurements. An In Vitro Study Using Modern Ultrasound Scanners. J Ultrasound Med 2009; 28:1511–1518

Document title: VasQ FDA pivotal Protocol	Document No. CD0121	Revision 12.0 14 March 2021	Page 14 of 42
--	------------------------	-----------------------------------	------------------

None of the following conditions are met at 180 days:

- Flow \geq 500 (-50) ml/min
- Thrill is palpable and bruit is audible
- Patient is receiving dialysis through the fistula

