7.11 Special COVID-19 pandemic instructions

1. In the event an on-site visit is not possible due to hospital restrictions or subject refusal to attend visit:
 - a. Conduct a phone visit (preferably using video with participation of investigator and subject). Use the relevant study follow-up worksheets to document the data. Please insert a note on the worksheet that the visit was performed by phone and not on-site.
 - b. Review the subject's medical record in detail to identify any adverse events, diagnostic fistulogram, interventions on the study fistula, placement of additional accesses, etc.
 - c. If dialysis records are not accessible in the EMR, please call the dialysis unit and collect the study required data. Please document the call in a dated and signed note.
 - d. Upload obtained data into the EDC using the Unscheduled Visit forms - Access site Assessment and Dialysis.
 - e. Report a protocol deviation of the follow-up visit out of window (if relevant) and Phone visit in EDC and record this in the protocol deviation log. Please add a comment in the comment field explaining that the deviation was caused by the restrictions related to COVID-19.
2. Once restrictions are lifted, the requirement for completing missing on-site visits based on subject status and progress in the study will be assessed.
3. End of Study should not be declared if X-Ray is missing even if all other data is available. The subject should return for X-Ray imaging as soon as possible before exiting the study.

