10.4 Sample size justification

Presentation of sample size in this trial is based on the observed Primary Patency rate meeting a PG of 55% (see Section 10.1). Based on limited historical information on the use of VasQ our conservative estimate of device performance is a Primary Patency rate of 70%. A sample of N = 116 evaluable subjects will provide 90% power to demonstrate VasQ meeting the PG. To account for an approximate 10% dropout rate, 129 subjects will participate in this trial. Power computations are based on Exact Binomial computations with a two-sided Alpha = 0.05, designed to demonstrate that the lower

Document title: VasQ FDA pivotal Protocol	Document No. CD0121	Revision 12.0 14 March 2021	Page 36 of 42
--	------------------------	-----------------------------------	------------------

bound of the 95% Exact Binomial confidence interval about observed Primary Patency is above the 55% PG.

In summary, $N = 129$ subjects will be included in this trial to provide 90% power to demonstrate that the VasQ meets its PG.

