10.6.3 Primary effectiveness analysis

The primary effectiveness endpoint, Primary Patency at 6 months post procedure, will be tested in the FAS_primary using the following hypotheses:

- $H_0: (\text{Primary Patency Rate})_{\text{observed}} \leq 55.0\%$
- $H_1: (\text{Primary Patency Rate})_{\text{observed}} > 55.0\%$

Hypotheses will be tested using a two-sided, 95% Exact Binomial confidence interval about the observed 6-month Primary Patency rate. We will declare success on this endpoint if the lower limit of the confidence interval is above 55.0%. Note that if there will be missing values and MI will be applied, we will apply Exact Binomial computations to each of the multiple data sets, then use SAS® PROC MIANALYZE to obtain a P-value for the combined results.

10.6.4 [REDACTED] Secondary Analysis

The [REDACTED] secondary effectiveness endpoint, Primary Patency at 6 months post procedure, will be tested in the FAS_secondary using the following hypotheses:

Document title: VasQ FDA pivotal Protocol	Document No. CD0121	Revision 12.0 14 March 2021	Page 38 of 42
--	------------------------	-----------------------------------	------------------

- H_0 : (Primary Patency Rate)_{observed} \leq 55.0%
- H_1 : (Primary Patency Rate)_{observed} $>$ 55.0%

Testing will be done only if the null of the primary hypothesis in the preceding section will have been rejected (i.e. hierarchical testing). The statistical method used for testing will be identical to that of the primary hypothesis.

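### The dialysis-status comparison in 10.6.8 uses a score with a confirmation route more open to subjects on dialysis, so at equal true patency that group can score higher when 6-month visits are missed

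*Combined protocol and SAP*

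**What the plan says.** Section 10.6.8 fits a logistic regression of the primary endpoint score on each covariate in turn. It reads the result as a performance contrast: "For the above we will be comparing device performance between levels defined on the covariate". Dialysis status is on the covariate list without a time point; only the vessel diameters are labelled baseline. The section adds that the trial is not powered for subgroup differences and that descriptive statistics will carry most of the information.

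Section 6.1 scores a subject as a success if there is no intervention to 180 days and any one of three conditions holds: Doppler flow at the threshold, palpable thrill with audible bruit, or "Patient is receiving dialysis through the fistula at 6 months". A note protects subjects who do not use the fistula: "if patient is not receiving dialysis through the fistula at 6 months, this will not indicate failure".

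Section 7.11 covers visits that cannot take place on site. It asks for a telephone visit and a detailed medical-record review, and adds: "If dialysis records are not accessible in the EMR, please call the dialysis unit and collect the study required data".

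Three other sections bear on the point. Section 10.5.2 scores a subject with no 6-month patency result as a success if patency without intervention is seen at a later visit. Sections 10.5.2 and 10.6.3 refer to multiple imputation. Section 10.5.5 defines one subset by dialysis at the index procedure and another that also includes subjects who start dialysis during the study.

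**The concern.** For this one covariate, a level of the covariate largely decides who can use one of the success routes. Conditions 1 and 2 are open to everyone, but the visit procedures describe them as examinations (ultrasound, palpation, stethoscope). Condition 3 is open only to a subject dialysed through the study fistula at 6 months, and a telephone call to the dialysis unit can establish it. When a 6-month visit is missed, conditions 1 and 2 tend to be lost in both groups, while condition 3 survives mainly in subjects already on dialysis at entry. The note in 6.1 prevents non-use from counting as failure. It does not supply the missing confirmation.

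At stake is the reading of an obvious subgroup table. Part of a higher patency rate in dialysis subjects could come from how patency was ascertained, and the plan includes nothing that would let a reader separate that part from a real difference. If status were taken at 6 months and not at entry, the covariate would also overlap with condition 3 itself.

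**Working it through.** **The plan's own figure.** The documents give no figure for the dialysis-status comparison. The nearest is the primary sample size: "A sample of N = 116 evaluable subjects will provide 90% power to demonstrate VasQ meeting the PG", on the basis that "Power computations are based on Exact Binomial computations with a two-sided Alpha = 0.05". With n = 116, the smallest count whose exact 95% lower limit exceeds 55% is 75 (64.7%, lower limit 55.24%). The one-tail error is 0.0222 and power at 70% is 0.911. Enrolment is 116/0.9 = 128.9, so 129. The plan's figure reproduces, and nothing below changes it.

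**Inputs for the illustration.** All except p are assumptions.
- p = 0.70, true intervention-free patency, equal in both groups (the design value in 10.4).
- u = share of each group with no examination at 6 months: 10% or 20%.
- w = 0.8, share of patent fistulas in use for dialysis at 6 months in the on-dialysis group; v = the same share in the other group, first set to 0.
- f = share of failures among unexamined subjects that are known from records, first set equal in both groups.
- Subjects with neither success nor failure established are treated as missing.

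**Base case.** Successes are p(1 − u + uw) on dialysis and p(1 − u) off dialysis. Failures are (1 − p)(1 − u + uf) in both. Hence OR = (1 − u + uw)/(1 − u), free of p and f.
- u = 10%: (0.90 + 0.08)/0.90 = 1.09
- u = 20%: (0.80 + 0.16)/0.80 = 1.20

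As rates, with f = 0:
- u = 10%: 0.686/(0.686 + 0.27) = 71.8% against 0.63/(0.63 + 0.27) = 70.0%
- u = 20%: 0.672/(0.672 + 0.24) = 73.7% against 0.56/(0.56 + 0.24) = 70.0%

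**Later-visit rule (10.5.2).** Let r be the share of still unconfirmed patent fistulas scored as success from a later visit. OR = (1 − u + uw + u(1 − w)r)/(1 − u + ur). With r = 0.5:
- u = 10%: 0.99/0.95 = 1.04
- u = 20%: 0.98/0.90 = 1.09

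**Subjects who start dialysis later.** OR = (1 − u + uw)/(1 − u + uv). At u = 20%:
- v = 0.25: 0.96/0.85 = 1.13
- v = 0.5: 0.96/0.90 = 1.07

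**Failures also found through dialysis records.** Let f1 apply on dialysis and f0 off dialysis. OR = [(1 − u + uw)/(1 − u)] × [(1 − u + u·f0)/(1 − u + u·f1)]. At u = 20%:
- f1 = 0.9, f0 = 0.5: 1.20 × 0.90/0.98 = 1.10
- f1 = 0.8, f0 = 0: 1.20 × 0.80/0.96 = 1.00
- f1 = 1, f0 = 0: 1.20 × 0.80/1.00 = 0.96

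**Scale.** With an assumed 58 subjects per group, a gap of about 21 points (70% against 90.6%) is needed for 80% power. In a simulation with an assumed 65 and 64 subjects and f = 0.67, a nominal 5% test rejects about 5% of the time at u = 10% and 7% at u = 20%, against 4.8% with no artefact.

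**Check on the remedy.** If successes known only from dialysis use are dropped but all known failures are kept, then at u = 20%, f1 = 0.9 and f0 = 0.5 the OR is 0.90/0.98 = 0.92, a bias against dialysis subjects. If successes and failures both come only from sources open to both groups, numerator and denominator match and the OR is 1 by construction. This requires equal examination rates and equal record-review yield in the two groups.

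**The case against.** The case against is substantial, and much of it stands.

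- A reader might infer that an unexamined off-dialysis subject can never be a success. Section 10.5.2 says otherwise: later observed patency without intervention counts.
- A reader might take the closing clause of 6.1, where failure means that none of the conditions is met, as making unconfirmed subjects failures. At p = 0.70 that would give odds ratios of 1.28 and 1.61 at 10% and 20% unexamined. Section 10.5.2 treats an absent 6-month result as missing, and 10.6.7 reserves missing-as-failure for the worst-case sensitivity analysis, so the documents do not support this as the main reading.
- A reader might infer that the artefact always favours dialysis subjects. That needs equal detection of failures. The same dialysis-unit call can reveal failures, and the working shows the effect vanishing or reversing.
- The documents give no rate of missed 6-month examinations. The only related figure is the dropout allowance of about 10%. Section 6.1 expects subjects who miss Doppler still to have thrill and bruit assessed, and 7.11 provides an access-site assessment form for telephone visits. If conditions 1 and 2 confirm every patent fistula, the effect is zero.
- Status at entry is the natural reading of the covariate, since dialysis status is collected at screening. The missing time point alone is only a gap in detail.
- The comparison is unpowered and mainly descriptive, and no success criterion depends on it.

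What survives is that the score is ascertained differently across the levels of this covariate, and no planned analysis addresses it. Descriptive rates carry the same distortion as a test, and low power does not remove it.

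**Conclusion.** The concern holds as a possible and modest distortion of one secondary analysis. At equal true patency, the on-dialysis group can score higher when 6-month examinations are missed. Under the stated assumptions (unconfirmed treated as missing, equal failure detection, 80% of patent fistulas in use in one group and none in the other), the spurious odds ratio is about 1.09 at 10% unexamined and 1.20 at 20%, before later-visit recovery. It moves toward 1 with that recovery, with multiple imputation and with subjects who start dialysis during the study. Its direction is not guaranteed. It could not be told apart from a real difference in the planned output. The primary test, sample size and power are unaffected.

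**What to change.** In 10.6.8, for the dialysis-status covariate only:

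1. State that status is taken at the index procedure, as in the Ongoing Dialysis Subset of 10.5.5.
2. Keep the planned model on the full 6.1 score and add one model on a score ascertained the same way in both groups. Success is by condition 1 or 2 only. Failure is by intervention before day 180, found through the medical-record review that applies to all subjects, or by on-site examination. Subjects whose success or failure is known only from dialysis-unit records are treated as missing. Restricting failures as well as successes matters, because trimming successes alone creates the opposite bias.
3. Tabulate successes by confirmation route and dialysis status, so that readers can see how many rest on condition 3 alone.

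The cost is a few sentences, one extra model and one table on data already collected, with a slightly wider interval for this covariate. The added model still assumes similar examination rates in the two groups, so report those rates beside it. The primary analysis does not change.

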10.6.9 Poolability analyses

10.6.9.1 Poolability Analysis: Main vs. Supplementary Cohort

Poolability between the main and supplementary cohorts, with respect to the primary patency rate, will be checked on the FAS secondary analysis set. The poolability will be tested using logistic regression for observed data only. [REDACTED]

10.6.9.2 Site poolability analysis

Descriptive statistics for primary patency rate will be provided by site. Site poolability will be tested by logistic regression [REDACTED]

10.6.10 Interim analysis

There is no planned interim analysis.

11 DATA COLLECTION, STUDY MONITORING, AND DATA DISCLOSURE

11.1 Data collection

Electronic CRFs (eCRFs) using data capture will be utilized. Site staff will enter the information required by the protocol onto eCRFs using a validated software/database that conforms to FDA requirements for electronic data capture. All data fields will be completed. However, if data are not available (i.e., missed visit, etc.), the site will receive instruction regarding electronic documentation. As data are entered, automated cross-check programs will search for any data discrepancies in the

Document title: VasQ FDA pivotal Protocol	Document No. CD0121	Revision 12.0 14 March 2021	Page 41 of 42
--	------------------------	-----------------------------------	------------------

eCRFs. Appropriate error messages will be generated, allowing for the modification or verification of the entered data. Queries will generally be sent to the investigational site using an electronic data query system that includes an automated audit trail of the corrections.

Monitoring personnel of sponsor or its designee, will review the eCRFs for completeness and accuracy and will instruct site personnel to make any corrections or additions. The Investigator, or designee, will certify that the data are complete and accurate by applying an electronic signature to the eCRF. Any subsequent alterations, corrections, or additions will be reviewed and electronically signed by the Investigator prior to database lock.

11.2 Concomitant Medications

Concomitant medication will be recorded throughout the duration of the study. A baseline medication regimen for each patient will be determined during the screening visit, and subsequent changes will be recorded during each on-site follow-up visit (refer to Table 7-1 for procedures timeline). The baseline medication regimen will include all medications prescribed for the purpose of treating chronic conditions. During on-site follow-up visits the following will be recorded:

- Changes to the regimens of all medications listed in the baseline (e.g. dosage, frequency). Regimen changes will be recorded in the EDC in the following manner:
 1. Enter an *end date* for the old regimen
 2. Open a new medication record for the change in regimen
 - Medications administered to treat AE's/SAE's, in accordance with the AE reporting as described in sections 8.1 and 8.4.
 - New medications prescribed to treat chronic conditions.

11.3 Imaging and Core Lab

The following images will be collected and uploaded to MMI (Core lab service provider):

- Ultrasound DICOMS
- X-Ray DICOMS
- All DICOMS from endovascular procedures (Intervention / diagnostic)

Ultrasound scans will be conducted according to ultrasound instructions document (CL007).
X-Ray will be conducted according to X-Ray acquisition guidelines (CD-CA-0040, previously CL008).
All images will be transferred to MMI for storage and evaluation in accordance with the Image Transfer Protocol and will be stored in a validated, electronic database consistent with 21 CFR Part 11. Access to images and associated study data will be restricted to authorized personnel only.

11.4 Site qualification

A site visit will be performed by sponsor or designee prior to the start of the study to review the protocol in detail, to ensure the availability of appropriate trial personnel, adequate resources and to assess their ability to properly conduct the study according to ICH-GCP guidelines and local requirements.

Document title:
VasQ FDA pivotal Protocol

Document No.
CD0121

Revision
12.0
14 March 2021

Page
42 of 42

11.5 Study monitoring and source data verification

The sponsor or designee will monitor the study to meet monitoring Standard Operating Procedures (SOPs), ICH-GCP guidelines, and applicable regulatory requirements and to ensure that study initiation, conduct, and closure are adequate.

11.6 Publication

The Sponsor and investigators plan to publish the outcomes of this study. Publication in writing and/or orally will take place after completion of the 6 months data collection and analysis or sooner if the study is terminated. Publication arrangements are detailed in the CTAs.

12 CLINICAL EVENTS COMMITTEE AND DATA SAFETY MONITORING BOARD

An independent clinical events/data safety committee will be formed to review abstracted clinical data and determine when the safety endpoints (steal, infection, aneurysm, seroma) have been met according to protocol definitions. The committee will comprise 3 physicians, who will not participate in the enrollment or treatment of subjects in this trial. In addition to the above listed safety endpoint components, all events of fistula failure and/or intervention will be reviewed by the committee and assessed for device relatedness. Any such event will trigger the accumulation of a portfolio of pertinent documents from the hospital admission. These documents will be collected and copies distributed to members of the CEC Committee. The interpretation of the event as classified and adjudicated by the clinical events committee will be used in the safety analysis.

In addition, the committee will review the progress of the trial following the enrollment of subjects and as requested on an ad hoc basis, to ensure that subject safety is not being compromised.
